12.6.1 Analysis Plans for Primary Objective

See section 12.3.

12.6.2 Analysis Plans for Secondary Objectives

See section 12.3.

12.6.3 Subgroup Analyses

There are no subgroup analyses planned

12.6.4 Other Planned Analyses

There are no other planned analyses.

13. TRIAL MANAGEMENT

13.1 Data and Safety Monitoring Plan (DSMP)

The Data and Safety Monitoring Committee (DSMC) of The University of Michigan Rogel Cancer Center is responsible for monitoring the safety and data integrity of the trial.

Big Ten CRC AHQ oversight activities include:

- Review and process all adverse events requiring expedited reporting as defined in the protocol

- Provide timely reports to MICHR-MIAP ([contact]) that require expedited reporting
- Notify participating sites of adverse events requiring expedited reporting
- Provide trial accrual progress, safety information, and data summary reports to the sponsor-investigator and MICHR-MIAP
- Coordinate quarterly meetings for this phase II study. These meetings will include each accruing site's principal investigator, clinical research specialist and/or research nurse (other members per principal investigator's discretion).
- The quarterly study team meetings will discuss matters related to:
 - Enrollment rate relative to expectations, characteristics of participants
 - Safety of study participants (Serious Adverse Event reporting)
 - Adherence to protocol (protocol deviations)
 - Completeness, validity and integrity of study data
 - Retention of study participants
- These meetings are to be documented by the site data manager or study coordinator using the Protocol Specific Data and Safety Monitoring Report (DSMR), signed by the site principal investigator or designated co-investigator. Big Ten CRC AHQ will assist in this process. The DSMR can be found in the Documents/Info tab of the EDC. Each site is required to submit the completed DSMR to Big Ten CRC AHQ on a quarterly basis together with other pertinent documents for submission to the DSMC.

13.2 University of Michigan Data Safety Monitoring Committee

The DSMC will review the information included on the DSMRs from the first subject enrolled until the last subject has completed the study drug interventions. Documentation of DSMC reviews will be provided to sponsor-investigator and Big Ten CRC AHQ. Issues of immediate concern by the DSMC will be brought to the attention of the sponsor-investigator and other regulatory bodies as appropriate. The sponsor-investigator will work with Big Ten CRC AHQ and MICHR-MIAP to address the DSMC's concerns.

The DSMC will provide the sponsor-investigator and Big Ten CRC AHQ evidence of its review. Big Ten CRC AHQ will distribute this information to the participating sites for submission to their respective IRB per the local IRB's policies and procedures.

13.3 Data Quality Oversight Activities

Remote validation of the EDC system data will be completed on a continual basis throughout the life cycle of the study. A summary report (QC Report) of these checks together with any queries resulting from manual review of the eCRFs will be generated for each site and transmitted to the site and the site monitor. Corrections will be made by the study site personnel.

Monitoring visits to the trial sites will be made periodically during the trial to ensure key aspects of the protocol are followed. Additional for cause visits may occur as necessary. Source documents will be reviewed for verification of agreement with data entered into the EDC system. It is important for the site investigator and their relevant personnel to be available for a sufficient amount of time during the monitoring visits or audit, if applicable. The site investigator and institution guarantee access to source documents by Big Ten CRC AHQ or its designee.

The trial site may also be subject to quality assurance audit by Bristol-Myers Squibb or its designee as well as inspection by appropriate regulatory agencies.

13.4 Compliance with Trial Registration and Results Posting Requirements

Under the terms of the Food and Drug Administration Modernization Act (FDAMA) and the Food and Drug Administration Amendments Act (FDAAA), the sponsor-investigator of the trial is solely responsible for determining whether the trial and its results are subject to the requirements for submission to the Clinical Trials Data Bank, <http://www.clinicaltrials.gov>. All results of primary and secondary objectives must be posted to CT.gov within a year of completion. The sponsor-investigator has delegated responsibility to Big Ten CRC AHQ for registering the trial and posting the results on clinicaltrials.gov. MICHR-MIAP will be responsible for submitting FDA Form 3674 to the FDA. Information posted will allow subjects to identify potentially appropriate trials for their disease conditions and pursue participation by calling a central contact number for further information on appropriate trial locations and study site contact information.

14. DATA HANDLING AND RECORD KEEPING

14.1 Data Management

Big Ten CRC AHQ will serve as the Clinical Research Organization for this trial. Data will be collected through a web-based clinical research platform compliant with Good Clinical Practices and Federal Rules and Regulations. Big Ten CRC AHQ personnel will coordinate and manage data for quality control assurance and integrity. All data will be collected and entered into the EDC system by study site personnel from participating institutions.

14.2 Case Report Forms and Submission

Generally, clinical data will be electronically captured in the EDC system and correlative results will be captured in the EDC system or other secure database(s). If procedures on the study calendar are performed for standard of care, at minimum, that data will be captured in the source document. Select standard of care data will also be captured in the EDC system, according to study-specific objectives. Please see the Data and Safety Oversight Process (DSOP) guidelines for further details.

The completed dataset is housed at Big Ten CRC AHQ and is the sole property of the sponsor-investigator's institution. It should not be made available in any form to third parties, except for authorized representatives of appropriate Health/Regulatory Authorities, without written permission from the sponsor-investigator and Big Ten CRC AHQ. After the initial publication, the complete data set will be available to all Big Ten CRC institutions.

14.3 Record Retention

To enable evaluations and/or audits from Health Authorities/Big Ten CRC AHQ, the site investigator agrees to keep records, including the identity of all subjects (sufficient information to link records; e.g., hospital records), all original signed informed consent forms, copies of all source documents, and detailed records of drug disposition. All source documents are to remain in the subject's file and retained by the site investigator in compliance with local and federal regulations. No records will be destroyed until Big Ten CRC AHQ confirms destruction is permitted.

14.4 Confidentiality

There is a slight risk of loss of confidentiality of subject information. All records identifying the subjects will be kept confidential and, to the extent permitted by the applicable laws and/or regulations, will not be made publicly available. Information collected will be maintained on secure, password protected electronic systems. Paper files that contain personal information will be kept in locked and secure locations only accessible to the study site personnel.

Subjects will be informed in writing that some organizations including the sponsor-investigator and his/her research associates, Big Ten CRC AHQ, Bristol-Myers Squibb IRB, or government agencies, like the FDA, may inspect their medical records to verify the information collected, and that all personal information made available for inspection will be handled in strictest confidence and in accordance with local data protection laws.

If the results of the study are published, the subjects's identity will remain confidential.

15. ETHICS

15.1 Institutional Review Board (IRB) Approval

The final study protocol and the final version of the informed consent form must be approved in writing by an IRB. The site investigator must submit written approval by the IRB to Big Ten CRC AHQ before he or she can enroll subjects into the study.

The site investigator is responsible for informing the IRB of any amendment to the protocol in accordance with local requirements. In addition, the IRB must approve all advertising used to recruit subjects for the study. The protocol must be re-approved by the IRB as local regulations require.

Progress reports and notifications of adverse events will be provided to the IRB according to local regulations and guidelines.

15.2 Ethical Conduct of the Study

The study will be performed in accordance with ethical principles originating from the Declaration of Helsinki. Conduct of the study will be in compliance with ICH Good Clinical Practice, and with all applicable federal (including 21 CFR parts 56 & 50), state, or local laws.

15.3 Informed Consent Process

The site investigator will ensure the subject is given full and adequate oral and written information about the nature, purpose, possible risks and benefits of the study. Subjects must also be notified they are free to discontinue from the study at any time. The subject should be given the opportunity to ask questions and allowed time to consider the information provided.

The subject's signed and dated informed consent must be obtained before conducting any procedure specifically for the study. The site investigator must store the original, signed informed consent form. A copy of the signed informed consent form must be given to the subject.

17. APPENDICES

17.1 Management of toxicities

These general guidelines constitute guidance to the Site Investigator and may be supplemented by discussions with the Sponsor Investigator. The guidance applies to all immuno-oncology (I-O) agents and regimens. A general principle is that differential diagnoses should be diligently evaluated according to standard medical practice. Non-inflammatory etiologies should be considered and appropriately treated. Corticosteroids are a primary therapy for immuno-oncology drug-related adverse events. The oral equivalent of the recommended IV doses may be considered for ambulatory patients with low-grade toxicity. The lower bioavailability of oral corticosteroids should be taken into account when switching to the equivalent dose of oral corticosteroids. Consultation with a medical or surgical specialist, especially prior to an invasive diagnostic or therapeutic procedure, is recommended. The frequency and severity of the related adverse events covered by these algorithms will depend on the immuno-oncology agent or regimen being used.

17.1.1 Gastrointestinal toxicity management

Gastrointestinal Adverse Event Management		
Rule out noninflammatory causes. If a noninflammatory cause is identified, treat accordingly and continue nivolumab therapy. Opiates/narcotics may mask symptoms of perforation. Infliximab should not be used in cases of perforation or sepsis.		
Grade of Diarrhea/Colitis	Management	Treatment and Follow-Up
Grade 1: Diarrhea:<4 stools/day over baseline; Colitis: asymptomatic	
 – Continue cabiralizumab and nivolumab therapy per protocol – Symptomatic treatment 	
 – Close monitoring for worsening symptoms – Educate patient to report worsening immediately 
If worsens:
 
 – Treat as Grade 2 or 3/4
Grade 2: Diarrhea: 4–6 stools per day over baseline; IV fluids indicated <24 hours; not interfering with ADL; Colitis: abdominal pain; blood in stool	
 – Delay cabiralizumab and nivolumab per protocol^a – Symptomatic treatment 	
If improves to Grade 1 ≤4 days:
 
 – Resume cabiralizumab and nivolumab therapy per protocol 
If persists ≥5–7 days or recurs:
 
 – 0.5–1 mg/kg/day methylprednisolone or oral equivalent – When symptoms improve to Grade 1, taper steroids over at least 1 month, consider prophylactic antibiotics for opportunistic infections, and resume cabiralizumab and nivolumab therapy per protocol 
If worsens or persists >3-5 days with oral steroids:
 
 – Treat as Grade 3 or 4

Grade 3–4: Diarrhea (G3): ≥7 stools per day over baseline; incontinence; IV fluids ≥24 hours; interfering with ADL; Colitis (G3): Severe abdominal pain, medical intervention indicated, peritoneal signs
 
Grade 4: Life-threatening, perforation
	
 – Delay or Discontinue cabiralizumab and nivolumab therapy per protocol^b – 1 to 2 mg/kg/day methylprednisolone IV or IV equivalent^c – Add prophylactic antibiotics for opportunistic infections – Consider lower endoscopy if clinically indicated 	
If Grade 3 AE improves to Grade 1 or baseline within 28 days:
 
 – Taper steroids over at least 1 month – Resume dosing of cabiralizumab and Nivolumab 
If Grade 4:
 
 – Permanently discontinue cabiralizumab and Nivolumab – Continue steroids until Grade 1, then taper steroids over at least 1 month 
If persists >3-5 days, or recurs after improvement:
 
 – Add infliximab 5 mg/kg (if no contraindications) – Follow up until resolution – Note: Infliximab should not be used in cases of perforation or sepsis

- If the AE requiring dose delay was due to one of the study drugs, the non-offending drug may be continued, taking into account the safety and clinical benefit to the patient
- If the AE requiring discontinuation was due to one of the study drugs, the non-offending drug may be continued, if there is timely resolution of AE and clinical benefit is shown by patient
- Patients on IV steroids may be switched to an equivalent dose of oral corticosteroids (e.g. prednisone) at start of tapering or earlier, once sustained clinical improvement is observed. Lower bioavailability of oral corticosteroids should be taken into account when switching to the equivalent dose of oral corticosteroids.

17.1.2 Hepatic toxicity management without liver metastasis

Hepatic Adverse Event Management without Liver Metastasis		
Rule out noninflammatory causes. If a noninflammatory cause is identified, treat accordingly and continue nivolumab therapy. Consider imaging for obstruction.		
Grade of Liver Test Elevation	Management	Follow-Up
AST or ALT >3.0x ULN and Total bilirubin >2x ULN or INR > 1.5	
 – Discontinue cabiralizumab and nivolumab per protocol – Start steroids 	
 – Continue LFT monitoring per protocol until resolution. – Continue monitoring for and other associated clinical signs or symptoms – Contact the Sponsor Investigator – Evaluate for non drug related causes of the laboratory abnormalities (e.g. obstruction, viral infection, Gilbert’s disease, etc) – Under selected circumstances (e.g alternative etiology is identified), patient may receive additional therapy only after consultation and agreement between the Sponsor/MM and the investigator if receiving additional treatment with cabiralizumab and nivolumab is in the best interest of the patient (e.g if the subject has demonstrated a response to therapy)
AST or ALT > 5 to ≤ 12 xULN and Total bilirubin ≤ 2 xULN	
 – Continue cabiralizumab and nivolumab therapy if there are no clinical signs of significant muscle or hepatic damage – Increase frequency of monitoring of AST, ALT, bilirubin, alkaline phosphatase and INR (every 48-72 hours or more frequently, as clinically indicated) – Monitor for other clinical symptoms (fatigue, nausea, vomiting, abdominal pain, fever, rash, and/or eosinophilia) 	
 – Contact the Sponsor Investigator if there are clinical signs of muscle or hepatic injury or other clinical symptoms – Contact the Sponsor Investigator if there is a concurrent increase of bilirubin, AST, ALT, or alkaline phosphatase – Notify the Sponsor Investigator if there is an AST or ALT increase > 5 xULN – Frequency of retesting can decrease to once a week or less if abnormalities stabilize or the trial drug has been discontinued and the subject is asymptomatic – Consider gastroenterology or hepatology referral
AST or ALT > 12 to ≤ 20 xULN and Total bilirubin ≤ 2 xULN or Isolated total bilirubin > 2 to ≤ 3 xULN	
 – Delay cabiralizumab and nivolumab therapy per protocol^a – Increase frequency of monitoring of (including but not limited to) AST, ALT, bilirubin, alkaline phosphatase and INR (every 48-72 hours or more frequently, as clinically indicated) – If there is a 2-fold ALT increase compared to the previous measurement, start steroids immediately – Consider steroid treatment on any total bilirubin increase of over 2.0x ULN – If there is a concurrent increase of alkaline phosphatase along with ALT, start steroids immediately – Monitor for other clinical symptoms (fatigue, nausea, vomiting, abdominal pain, fever, rash, and/or eosinophilia) 	
If AST/ALT return to ≤ 12 xULN within ≤ 7 days:
 
 – Resume routine monitoring – Resume cabiralizumab and nivolumab therapy at same dose level per protocol 
If elevations persist and remain at the same level > 7 days but < 28 days:
 
 – Start steroids immediately and discontinue further dosing – Continue monitoring and consider dosing the subject with nivolumab therapy at the same dose level 
Consider tapering steroids over at least 1 month
 
If elevations persist at the same level > 28 days or worsen:
 
 – Discontinue cabiralizumab and nivolumab therapy per protocol – 0.5-1 mg/kg/day methylprednisolone or oral equivalent and when LFT returns to Grade 1 or baseline, taper steroids over at least 1 month – Consider prophylactic antibiotics for opportunistic infections – Discuss with Sponsor Investigator

Hepatic Adverse Event Management without Liver Metastasis		
Rule out noninflammatory causes. If a noninflammatory cause is identified, treat accordingly and continue nivolumab therapy. Consider imaging for obstruction.		
Grade of Liver Test Elevation	Management	Follow-Up
AST or ALT > 20 xULN or Total bilirubin >3 xULN	
 - Discontinue cabiralizumab and nivolumab therapy^b - Increase frequency of monitoring to every 1 to 2 days - Consider 1 to 2 mg/kg/day methylprednisolone IV or IV equivalent^c - Consider adding prophylactic antibiotics for opportunistic infections - Consult gastroenterologist and hepatologist, if clinically indicated 	
If returns to Grade 2:
 
 - Consider steroid taper over at least 1 month if they have been started 
If does not improve in >3–5 days, worsens, or rebounds:
 
 - Consider adding mycophenolate mofetil 1 g BID - If no response within an additional 3–5 days, consider other immunosuppressants per local guidelines - Follow up until resolution

- a. If the AE requiring dose delay was due to one of the study drugs, the non-offending drug may be continued, taking into account the safety and clinical benefit to the patient.
- b. If the AE requiring discontinuation was due to one of the study drugs, the non-offending drug may be continued, if there is timely resolution of AE and clinical benefit is shown by patient.
- c. Patients on IV steroids may be switched to an equivalent dose of oral corticosteroids (e.g. prednisone) at start of tapering or earlier, once sustained clinical improvement is observed. Lower bioavailability of oral corticosteroids should be taken into account when switching to the equivalent dose of oral corticosteroids.

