17.1.3 Hepatic toxicity management with liver metastasis

Hepatic Adverse Event Management with Liver Metastasis		
Rule out noninflammatory causes. If a noninflammatory cause is identified, treat accordingly and continue nivolumab therapy. Consider imaging for obstruction.		
Grade of Liver Test Elevation	Management	Follow-Up
AST or ALT >3.0x ULN and Total bilirubin >2x ULN or INR > 1.5	
 - Discontinue cabiralizumab and nivolumab therapy per protocol - Start steroids 	
 - Continue LFT monitoring per protocol until resolution. - Continue monitoring for and other associated clinical signs or symptoms - Contact the Sponsor Investigator - Evaluate for non drug related causes of the laboratory abnormalities (e.g. obstruction, viral infection, Gilbert’s disease, etc) - Under selected circumstances (e.g alternative etiology is identified), patient may receive additional therapy only after consultation and agreement between the Sponsor/MM and the investigator if receiving additional treatment with cabiralizumab and nivolumab is in the best interest of the patient (e.g if the subject has demonstrated a response to therapy)
AST or ALT > 5 to ≤ 12 xULN and Total bilirubin ≤ 2 xULN	
 - Continue cabiralizumab and nivolumab therapy if there are no clinical signs of significant muscle or hepatic damage - Increase frequency of monitoring of AST, ALT, bilirubin, alkaline phosphatase and INR (every 48-72 hours or more frequently, as clinically indicated) - Monitor for other clinical symptoms (fatigue, nausea, vomiting, abdominal pain, fever, rash, and/or eosinophilia) 	
 - Contact the Sponsor Investigator if there are clinical signs of muscle or hepatic injury or other clinical symptoms - Contact the Sponsor Investigator if there is a concurrent increase of bilirubin, AST, ALT, or alkaline phosphatase - Notify the Sponsor Investigator if there is an AST or ALT increase > 5 xULN - Frequency of retesting can decrease to once a week or less if abnormalities stabilize or the trial drug has been discontinued and the subject is asymptomatic - Consider gastroenterology or hepatology referral

Hepatic Adverse Event Management with Liver Metastasis		
Rule out noninflammatory causes. If a noninflammatory cause is identified, treat accordingly and continue nivolumab therapy. Consider imaging for obstruction.		

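### In the two hepatic toxicity tables, the header continues nivolumab once a noninflammatory cause is found, while the first row stops both drugs and makes further dosing in that case subject to sponsor agreement

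*Combined protocol and SAP*

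**What the plan says.** Sections 17.1.2 (without liver metastasis) and 17.1.3 (with liver metastasis) each open with a header that applies to the whole table. It asks the site to rule out noninflammatory causes and continues: "If a noninflammatory cause is identified, treat accordingly and continue nivolumab therapy". It then adds: "Consider imaging for obstruction".

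The first row of each table covers AST or ALT above 3x ULN together with total bilirubin above 2x ULN or INR above 1.5. In 17.1.2 the action is "Discontinue cabiralizumab and nivolumab per protocol"; in 17.1.3 it is "Discontinue cabiralizumab and nivolumab therapy per protocol". Both rows start steroids. The follow-up column of the same row says "Evaluate for non drug related causes of the laboratory abnormalities (e.g. obstruction, viral infection", and Gilbert's disease is also listed. It then describes when dosing may go on: "Under selected circumstances (e.g alternative etiology is identified"), the "patient may receive additional therapy only after consultation and agreement between the Sponsor/MM and the investigator".

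Three other places bear on this:

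- The introduction to section 17.1 calls the tables guidance for the site investigator.
- Section 6.3 refers sites to 17.1 and 17.2 for instructions on stopping therapy and names hepatic toxicity.
- Section 12.3 stops enrollment at the interim analysis if 3 or more of 17 patients have Grade 4 events that make stopping treatment necessary under section 6.3.

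**The concern.** Header and row both speak to a patient whose liver abnormality has an identified cause other than immune-related toxicity, and they differ on what happens to nivolumab. Under the header it goes on without further step. Under the row it stops with cabiralizumab, and restarting needs agreement from outside the site. The header is also silent on cabiralizumab, so a site that follows it has no instruction for the second drug.

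Two sites could treat the same patient differently and each point to the protocol. The patients concerned have combined transaminase and bilirubin or INR elevation, so this is a safety matter. There is a possible knock-on effect for interim monitoring, because the second safety threshold depends on whether the protocol requires treatment to stop.

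**Working it through.** No figure in the plan needs reproducing. The check is a comparison of texts, followed by a worked case.

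**Step 1. Header and first row compared (17.1.2; 17.1.3 has the same content).**

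| Question | Header | First row |
|---|---|---|
| Is a non-drug or noninflammatory cause covered? | Yes; obstruction is named for imaging | Yes; obstruction, viral infection and Gilbert's disease are named |
| Nivolumab | Continue | Discontinue |
| Cabiralizumab | Not mentioned | Discontinue |
| Laboratory threshold | None | AST/ALT >3x ULN with bilirubin >2x ULN or INR >1.5 |
| Approval before further dosing | None | Sponsor/MM and investigator must agree |

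**Step 2. Do the terms overlap?** The header speaks of noninflammatory causes and the row of non-drug causes. These are not the same set: viral infection is non-drug but may be inflammatory. Obstruction falls in both and is named in both, so it is enough for a test case.

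**Step 3. Worked case.** A patient has ALT above 3x ULN and total bilirubin above 2x ULN, and imaging shows biliary obstruction. The row applies however its and/or condition is grouped, because both the transaminase and the bilirubin limits are exceeded. The header continues nivolumab. The row stops both drugs until agreement is reached.

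**Step 4. Does another clause settle it?**

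- Footnote b lets the non-offending drug continue, but only when the event is due to one of the study drugs. It is not attached to this row.
- The closing provision of 6.3 on continuing the other drug likewise assumes that one study drug caused the event.
- The 6.3 catch-all for Grade 4 events is limited to drug-related events not already addressed in 17.1. Hepatic events are addressed there.
- The definition of drug-induced liver injury in 11.1.6 expressly excludes cases with another apparent cause. The hepatic row contains no such exclusion.

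**Step 5. The other tables.** The header sentence appears in seven tables, 17.1.1 to 17.1.7. The sponsor-agreement clause for an alternative cause appears only in the first rows of 17.1.2 and 17.1.3. In the remaining 7 − 2 = 5 tables (gastrointestinal, renal, pulmonary, endocrine, skin) no row takes up the alternative-cause case, so header and rows can be applied one after the other.

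**Step 6. The interim threshold.** Suppose the worked case were Grade 4, fell among the first 17 patients, and two other patients already counted. Under the row the total is 2 + 1 = 3 and enrollment stops. Under the header it is 2 + 0 = 2 and this rule does not stop it. Section 12.3 limits its third rule (Grade 5) to drug-attributable events but puts no such limit on the second, so a non-drug cause does not by itself remove the event from the count. The documents assign no grade to the row, so this shows only that the count could depend on the reading.

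**The case against.** The strongest defence is that the header is a gate: noninflammatory causes are excluded first, and the rows then apply to immune-related events. The introduction to 17.1 supports this, since it asks for non-inflammatory causes to be considered and treated and presents steroids as therapy for drug-related events. This stands for the five non-hepatic tables. It fails for the first hepatic row, which itself deals with the patient whose alternative cause has been found and sets its own condition. Had the gate already removed that patient, the clause would have little left to govern.

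A second defence is that a specific row qualifies a general header. That is a reasonable way to read a protocol, but no rule of precedence is stated, and the header's opening instruction to rule out causes invites a site to apply it first.

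Third, the tables are described as guidance, and the row tells the site to contact the Sponsor Investigator. This lessens the practical risk. It does not remove it, because 6.3 relies on the tables for discontinuation and a site following the header may never reach that step.

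A reader might also infer more than the documents support:

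- **That all seven tables contradict themselves, for example through the Grade 4 gastrointestinal row.** That row says "Permanently discontinue cabiralizumab and Nivolumab", but it can be read as applying only after other causes are excluded.
- **That the hepatic row ends treatment permanently.** It does not use that word, and it allows further treatment with both drugs if agreement is reached.
- **That the interim safety rule is compromised.** No grade or event rate is given for this row. It is also true of any 3-of-17 rule that one patient can be decisive.

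**Conclusion.** The concern holds for the first row of 17.1.2 and of 17.1.3: two of the seven tables that carry the header, one row in each. The disagreement is over whether nivolumab continues without interruption or both drugs stop until the Sponsor/MM and the investigator agree. The header's silence on cabiralizumab is a related drafting gap, not an opposite instruction.

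The conclusion assumes only that obstruction is both a noninflammatory and a non-drug cause, as the two texts themselves suggest. The effect on the interim count further requires a Grade 4 event among the first 17 patients. Response thresholds, sample size and the stated error rates do not depend on this point. It merits correction because it concerns dosing in patients with combined liver abnormalities.

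**What to change.** In 17.1.2 and 17.1.3, reconcile the header with the first row so that they give the same instruction when a non-drug, noninflammatory cause is identified, or state which governs. Use one term for such causes in both places, and have the header say what happens to cabiralizumab as well as nivolumab. Which instruction applies is a clinical decision for the sponsor; nothing here favours either.

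Once that is settled, add a sentence to 6.3 or 12.3 saying whether a Grade 4 hepatic event with such a cause counts toward the second interim threshold.

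The cost is amendment wording in two tables and one sentence elsewhere. No new data, visits or patients are needed.
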